5.2.4.4. Change from Baseline in Stool Consistency (mBSFS-C or BSFS)

Stool consistency for a bowel movement is measured using the mBSFS-C for subjects in Group A and the BSFS for subjects in Group B. The weekly average stool consistency scores will be determined using the approach defined in [Section 3.3.7](#) with missing scores excluded as described in [Section 3.3.4](#) and presented for each week in the 4-week treatment period. The change from baseline in the average weekly stool consistency score will be analyzed in the FAS Population using a linear mixed-effects ANCOVA model with fixed effects for gender (stratification variable), treatment, week, the interaction of treatment and week, and the corresponding baseline value; a random intercept for subject will also be specified. Least Squares (LS) means, with 95% confidence intervals and the corresponding statistical p-value, will be presented for each week, and across all 4 weeks, of the 4-week treatment period for the difference between the difference in LS means for each of treatment groups versus placebo, combined active doses within each age group versus placebo, and overall active doses versus placebo. The analysis of interest for this secondary endpoint is the difference in LS means between each plecanatide group and placebo for the estimated overall average change from baseline across the 4-week treatment period.

The baseline stool consistency (mBSFS-C or BSFS) rate will be calculated as the equally weighted average of the average stool consistency (mBSFS-C or BSFS) rate for each of the two weeks preceding initiation of study drug.

The above analysis will be repeated for the PP Population.

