8.4 GENERAL CONSIDERATIONS

The final data analysis will be performed after all patients have either completed or have been discontinued from the study. The study will be unblinded after patient membership in each of the various analysis populations has been determined at a blinded data review meeting and upon confirmation of database lock.

Three treatment groups are identified for all analyses cited in the following as “by treatment group”: A (patients in Age Group A receiving plecanatide doses of 0.5 mg or 1.0 mg); B (patients in Age Group B receiving plecanatide doses of 1.0 mg, 2.0 mg, or 3.0 mg); Placebo (all patients randomized to receive placebo.)

Any deviations from the analyses presented here will be detailed in the clinical study report. All outputs will be produced using SAS® version 9.2 or later.

All efficacy data will be summarized and analyzed using the FAS and PP Populations unless otherwise noted. Safety data will be summarized using the Safety Population.

Imputation of missing data, where appropriate, will be performed as indicated for a given analysis. Any spurious or erroneous data will be queried and followed up until satisfactorily resolved; if not resolvable, the data will be set to missing. All data collected in the clinical database will be included in the data listings.

Summary statistics—number of patients (n), mean, standard deviation (SD), median, minimum, and maximum—will be presented for continuous variables. Frequencies and percentages will be presented for categorical variables. Unless otherwise noted, percentages will be calculated using the total number of patients in the appropriate population and/or subgroup and per treatment group where applicable. Where data are collected over time, both the observed data and change from the Screening Period (baseline) will be summarized at each time point.

Statistical testing including p-values and confidence intervals (CIs) will be presented as described in each section below. The Type I error rate (alpha) for the analysis of the primary efficacy endpoint is 0.05 (two-sided).

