8.8.2.2 Change from Baseline in Frequency of BMs, SBMs, and CSBMs, by Study Week

The weekly BM rate for each patient will be computed, as described in **Section 8.4.1**, for each week of the 4-week treatment period and for the two weeks of the follow-up period. A summary, by treatment group, of the mean weekly BM rate, and change from baseline in mean weekly BM rate, for each of the 6 study weeks will be presented. The change from baseline in mean weekly BM rate will be analyzed using a linear mixed-effects model with fixed effects for gender (stratification variable), treatment, week, the interaction of treatment and week, and the corresponding baseline value; a random intercept for patient will also be specified. The least squares (LS) mean change from baseline will be presented, by treatment group, and the difference in LS means for each treatment group, A, B, and A and B combined, versus Placebo, with 95% confidence intervals and corresponding statistical p-values.

Similarly, for the change from baseline in frequency of SBMs and CSBMs by study week.

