8.8.2.4 Change from Baseline in Stool Consistency (mBSFS-C or BSFS)

Stool consistency for a bowel movement is measured using the mBSFS-C for patients in Group A and the BSFS for patients in Group B. The weekly average stool consistency scores will be determined using the approach defined in **Section 8.4.1** and presented for each week in the 4-week treatment period; the baseline weekly average is determined as described in **Section 8.4.3**. The change from baseline in the average weekly stool consistency score will be analyzed in the FAS Population using a linear mixed-effects model with fixed effects for gender (stratification variable), treatment, week, the interaction of treatment and week, and the corresponding baseline value, and a random intercept for patient. Least Squares (LS) means, with 95% confidence intervals and the corresponding statistical p-value, will be presented for each week, and across all 4 weeks, of the 4-week treatment period for the difference between the difference in LS means for each of treatment groups A and B versus Placebo. The analysis of interest for this secondary endpoint is the difference in LS means between each plecanatide group and placebo for the estimated overall average change from baseline across the 4-week treatment period.

The above analysis will be repeated for the PP Population.

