5.2.2. Primary Efficacy Analysis

The weekly SBM rate for each subject will be computed for each week of the 4-week treatment period. The change from baseline in mean weekly SBM rate will be analyzed using a linear mixed-effects model with fixed effects for gender (stratification variable), treatment, week, the interaction of treatment and week, and the corresponding baseline value; a random intercept for subject will also be specified. The least squares (LS) mean change from baseline will be presented, by treatment groups, and the difference in LS means for each treatment group versus placebo and combined active doses within each age group versus placebo in a separate model for each age group, and overall active doses versus placebo in a separate model with 95% confidence intervals and corresponding statistical p-values.

The baseline SBM weekly rate will be the weekly average number of SBMs recorded during each of the 2 weeks preceding initiation of study drug.

The above analysis will be repeated for the PP Population.

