The weekly average abdominal pain and abdominal discomfort scores will be determined using the approach defined in [Section 3.3.7](#) with missing scores excluded as described in [Section 3.3.4](#) and presented for each week in the 4-week treatment period. The change from baseline in the weekly averaged abdominal pain and abdominal discomfort scores will be analyzed in the FAS Population using a linear mixed-effects ANCOVA model with fixed effects for gender (stratification variable), treatment, week, the interaction of treatment and week, and the corresponding baseline value; a random intercept for subject will also be specified. The least squares (LS) means, with 95% confidence intervals and the corresponding statistical p-value, will be presented for each week, and across all 4 weeks, of the 4-week treatment period for the difference between the difference in LS means for each of treatment group versus placebo, combined active doses within each age group versus placebo, and overall active doses versus placebo. The analysis of interest for this secondary endpoint is the difference in LS means between each plecanatide group (each dose within each age group, combined active dose within each age group, and overall active dose) versus placebo for the estimated overall average change from baseline in abdominal pain and abdominal discomfort scores across the 4-week treatment period.

Baseline abdominal pain and abdominal discomfort will be calculated as the equally weighted average of the average abdominal pain (or abdominal discomfort) for each of the two weeks prior to initiation of study drug.

The above analysis will be repeated for the PP Population.

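### The overall stool-consistency contrast mixes raw points from a 5-category and a 7-category scale, so its size cannot be read on either

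*Combined protocol and SAP*

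**What the plan says.** SAP 5.2.4.4 assigns one instrument to each age group: "Stool consistency for a bowel movement is measured using the mBSFS-C for subjects in Group A and the BSFS for subjects in Group B". Each week's score is the plain mean of the recorded values (SAP 3.3.7), and baseline is the plain mean of two weekly means. The mixed model has gender, treatment, week, treatment by week and baseline, with a random intercept. Besides the single-dose comparisons, it is to give estimates, confidence intervals and p-values for "combined active doses within each age group versus placebo, and overall active doses versus placebo", at each week and across the four weeks, in the FAS and again in the PP population.

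The sentence on priority reads "The analysis of interest for this secondary endpoint is the difference in LS means between each plecanatide group and placebo". It lacks the parenthesis found for abdominal pain in SAP 5.2.4.1, "each dose within each age group, combined active dose within each age group, and overall active dose". It also lacks the instruction in SAP 5.2.2 to fit "in a separate model for each age group, and overall active doses versus placebo in a separate model".

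Protocol 8.8.2.4 names, for this endpoint, only the "difference in LS means for each of treatment groups A and B versus Placebo". The parallel mixed-model endpoints in protocol 8.8.2 name the "difference in LS means for each treatment group, A, B, and A and B combined, versus Placebo".

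**The concern.** A change of one unit does not mean the same thing in the two age groups. If raw changes are averaged over both, the result depends on the age mix as well as on the drug, and a reader cannot translate it into stool form. At stake are the overall rows for this endpoint: five estimates (four weeks and the average) in each of two populations, so ten estimates with confidence intervals and p-values.

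A second question follows from the allocation. It is 2:1 in children and 3:1 in adolescents, so the pooled active and pooled placebo groups differ in age mix, and no model term accounts for it.

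**Working it through.** **Inputs from the documents.** Seven arms of 30 (SAP 3.2). This reproduces the planned size: 3 × 30 = 90 children, 4 × 30 = 120 adolescents, 210 in all. Active: 60 children and 90 adolescents. Placebo: 30 and 30. The documents give no SD, baseline mean, placebo change or effect size for stool consistency; the sample-size inputs concern SBM frequency only.

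**1. Matching the scales by the wording of Appendices C and D**

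| Stool | mBSFS-C | BSFS |
|---|---|---|
| Hard lumps | 1 | 1 |
| Lumpy sausage | 2 | 2 |
| Cracked surface | none | 3 |
| Smooth and soft | 3 | 4 |
| Soft blobs | none | 5 |
| Mushy | 4 | 6 |
| Watery | 5 | 7 |

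Protocol exclusion criterion 19 uses the same 4/6 and 5/7 pairs. Lumpy to smooth and soft is +1 for a child and +2 for an adolescent. Hard lumps to watery is +4 and +6.

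**2. The unit problem.** Suppose the drug produces exactly the lumpy-to-smooth change in every patient and placebo produces none.

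- Pooled, without an age term: 0.4 × 1 + 0.6 × 2 = 1.6.
- With an age term, each age group is weighted by (active × placebo)/total: children 60 × 30/90 = 20, adolescents 90 × 30/120 = 22.5. The weights are 20/42.5 = 0.471 and 0.529, and the result is 0.471 × 1 + 0.529 × 2 = 1.53.

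Neither 1.6 nor 1.53 is a change in mBSFS-C or BSFS points. In a stool-level simulation with one identical drug effect on stool form (assumed inputs), children showed about 0.28 points and adolescents about 0.48. The planned pooled model gave 0.44, and 0.39 with an age term.

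**3. The age-mix term.** Adolescents are 90/150 = 60% of active and 30/60 = 50% of placebo. With no drug effect the expected pooled difference is (0.60 − 0.50) × gap = 0.1 × gap, where gap is the adolescent minus the child mean change. A single seven-arm model that weights arms equally gives the same shares (3/5 and 1/2).

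**4. Does baseline adjustment remove it?** Simulated ANCOVA on the four-week mean with treatment, baseline and gender; no drug effect; assumed SD of change 0.8 to 1.0, baseline SD 0.6, slope of change on baseline −0.5, adolescent mean baseline higher by 0 to 0.3.

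| Gap | Bias | Type I error |
|---|---|---|
| 0.25 | 0.025 to 0.039 | 5.0 to 5.6% |
| 0.5 | 0.048 to 0.062 | 5.3 to 6.2% |
| 0.6 | 0.059 to 0.071 | 6.6% (SD 0.8), 5.8% (SD 1.0) |

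The gap-0.6 error rates are averages over the baseline offsets (6,000 runs per cell; 12,000 in the other rows). Adjustment did not remove the bias: it was unchanged when mean baselines were equal and larger when adolescents started higher. With an age term the bias was within about 0.003 of zero.

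**5. What gap is plausible?** In the stool-level simulation both age groups had the same underlying stool form, so the gap arose from coding alone.

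| Placebo change, child / adolescent | Gap | Bias | Type I error |
|---|---|---|---|
| 0.27 / 0.42 | 0.15 | 0.023 to 0.025 | 4.0 to 4.7% |
| 0.54 / 0.87 | 0.33 | 0.039 to 0.040 | 5.2 to 5.7% |
| 0.92 / 1.51 | 0.59 | 0.062 to 0.067 | 5.6 to 5.9% |

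**The case against.** The strongest reply is that little rests on this contrast. It is one comparison for one secondary endpoint in a trial declared exploratory, without multiplicity adjustment, and SAP 5.2.4.4 does not name it in its analysis of interest. Per-dose and within-age results are planned in any case. This stands, and it limits the weight of the point.

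The reply also holds that the age-mix bias is not about scales. That is right. SBM, BM and CSBM, fecal incontinence, defecation pain rate and large-diameter stools use the same pooled model without an age term. Different scales can widen the gap, but they do not create the mechanism.

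The missing separate-model wording is partly a drafting pattern. It is also absent from the pain and discomfort score paragraphs (SAP 5.2.4.1 and 5.2.4.7), and SAP section 5 lists each age group with its own placebo.

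A reader might infer more than the documents support:

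- *That the pooled estimate is meaningless or usually has the wrong sign.* It is a weighted mixture and still shows direction when effects are not near zero. A true −0.05 in both ages averaged +0.007 at a gap of 0.5, but the standard error is about 0.9 × √(1/150 + 1/60) = 0.14, so the two values cannot be told apart.
- *That type I error is seriously inflated.* Rates near 7% needed a gap of 1.0, beyond the largest gap (0.59) that coding alone produced.
- *That the protocol deliberately excluded the combined contrast and the SAP broke with it.* No reason for the omission is given, and protocol section 8 lets the SAP supersede it on all but the primary analysis. The protocol is also not a clean model, because its comparator is "Placebo (all patients randomized to receive placebo". That group is half on each scale, and would put −0.5 × gap into A versus placebo and +0.5 × gap into B.

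**Conclusion.** The point holds, mainly as a problem of interpretation. Followed as written, SAP 5.2.4.4 yields an overall LS-mean difference that mixes mBSFS-C and BSFS points and has no readable size on either scale. This part follows from the appendices and needs no assumption about the data. An age term alone does not repair it.

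The age-mix bias is secondary: about 0.03 to 0.07 points and a type I error of about 5 to 6.5% for gaps of 0.25 to 0.6. Those figures rest wholly on assumed SDs, baselines and placebo changes. The within-age contrasts are sound if fitted separately on one scale. The point is worth correcting because the correction is cheap, but it does not threaten the trial's main conclusions.

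**What to change.** In SAP 5.2.4.4:

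1. State that the models are fitted separately in Group A and Group B, on the native scale, each against its own-age placebo (wording as in 5.2.2 and 5.2.4.2), and that these contrasts are the analysis of interest. Do not import the protocol's all-ages placebo group.
2. Omit the overall contrast for this endpoint. Alternatively, keep it as supportive only, standardised within scale and with age group in the model.
3. Minor: say how Group B patients who rate on the children's scale are handled (SAP 3.3.7, those turning 12 between screening and randomization). About one is expected if ages are uniform: 90/6 = 15 children aged 11, and 15 × 28/365 ≈ 1.2.
4. Minor: correct the 14.2.6.x table titles, which name only the mBSFS-C.

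The cost is a few lines of SAP text and no new data. One pooled secondary result is lost or downgraded, and a standardised version would be in SD units rather than stool-form points.

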5.2.4.5. Use of Rescue Medication

The proportion of subjects who used at least one dose of rescue medication during the treatment period, will be summarized by treatment group. The number of tablets of rescue medication used per week, and overall, for the 4-week treatment period will be analyzed by treatment group. The Mann Whitney U Test (Wilcoxon Rank Sum Test) will be used to compare the difference between each treatment group, combined active doses within each age group, and overall active doses, versus Placebo at each week, and over all 4 weeks, of the 4-week treatment period.

The above analysis will be repeated for the PP Population.

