19. Patient reports having more than 1 loose, mushy stool (Diary-recorded stool consistency of 6 on the Bristol Stool Form Scale (BSFS or 4 on the modified Bristol Stool Form Scale for Children [mBSFS-C]) or any watery stool (Diary-recorded stool consistency of 7 on the BSFS or 5 on the mBSFS-C) with any SBM that occurred in the absence of laxative use on the calendar day of the BM or the calendar day before the BM during each 7-day (week) period before the randomization day and up to the day of randomization;
20. ≥ 3 CSBMs per week for either week of the 2-week baseline diary assessment immediately preceding the randomization visit;
21. > 6 SBMs per week for either week of the 2-week baseline diary assessment immediately preceding the randomization visit;
22. Patient reports worst abdominal pain intensity (WAPI) scores in the 2-week baseline diary that meet either of the following:
 - a. WAPI score of 0 on the 11-point Numeric Rating Scale or Wong-Baker Faces® Pain Rating Scale for more than two days during each week of the 2-week baseline diary period.
 - b. An average WAPI < 3 for either of the two weeks of the baseline diary;

23. Completion of < 5 of the 7 required daily diary entries in each week of the 2-week baseline diary assessment immediately preceding the randomization visit;
24. Use of rescue medication (Dulcolax®, bisacodyl) for more than 2 days during either of the two weeks of the 2-week baseline diary assessment immediately preceding the randomization visit.

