***Soiling of underwear in younger children may be indicative of Fecal Incontinence**

To remain eligible for the study, patients must complete at least 5 of the 7 days of electronic End-of-Day diary entries for each of the 2 weeks of Baseline diary period.

Compliance with diary entries should be a focus for patient education at the telephone contact visits and as needed per the judgement of the clinical site staff.

The following endpoints will be assessed using data collected via the electronic diary in “real time”:

• *Frequency of Bowel Movements*

Patients/caregivers will be asked to report each BM experienced.

• *Stool Consistency*

Patients/caregivers will be asked to rate the patient’s stool consistency according to the BSFS (see **Appendix C**) or mBSFS-C (see **Appendix D**), which will be provided to them in the form of a laminated card (and will appear on the appropriate electronic device) at the Screening Visit (Visit 1), and may be referred to as often as necessary throughout the Screening, Treatment and Post-treatment Periods. The BSFS and mBSFS-C are validated measures of stool consistency commonly used in clinical trials.

• *Stool Diameter*

Patients/caregivers will be asked to report the number of large diameter stools. A large diameter stool is defined as one that is large enough to clog the toilet.

• *Use of Rescue Medication (RM)*

Patients/caregivers will report the use of provided rescue medication (Dulcolax®), including time of use and amount of rescue medication used. Use of rescue medication will determine whether a BM was spontaneous, but only this aspect of rescue medication use is part of the primary endpoint.

The following endpoints will be assessed using data collected via the electronic diary at the end of the day:

• *Fecal Incontinence*

As part of the daily diary (end of day), the following question will be asked:

How many episodes of fecal incontinence did you experience today?

0 1 2 3 more than 3

• *IBS Symptoms*

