8.8.2.5 Use of Rescue Medication

The number of tablets of rescue medication used per week, and overall, for the 4-week treatment period will be analyzed by treatment group. The Mann Whitney U Test (Wilcoxon Rank Sum Test) will be used to compare the difference between each treatment group, A, B, and A and B combined, versus Placebo at each week, and over all 4 weeks, of the 4-week treatment period.

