3.2. RANDOMIZATION AND MASKING

This is a double-blind, placebo-controlled study with seven treatment age/dose groups that will be conducted at up to approximately 20 clinical sites. Subjects 6-11 years of age will be randomly assigned to 1 of 3 treatment groups (2 active treatments, 1 matching placebo) in a 1:1:1 ratio stratified by gender and subjects 12 to < 18 years of age will be randomly assigned to 1 of 4 treatment groups (3 active treatments, 1 matching placebo) in a 1:1:1:1 ratio stratified by gender using an Interactive Web-based Response System (IWRS).

Central, block randomization will be performed with stratification by gender.

Age Dose Group		Treatment		No. of Tablets to be Taken Daily	Dose Level	Number of Subjects
A	6 to 11 yrs. old	1	0.5 mg plecanatide	1	0.5 mg plecanatide	30
A	6 to 11 yrs. old	2	1.0 mg plecanatide	1	1.0 mg plecanatide	30

A	6 to 11 yrs. old	3	Matching placebo	1	placebo	30
B	12 to < 18 yrs. old	4	0.5 mg plecanatide	2	1.0 mg plecanatide	30
B	12 to < 18 yrs. old	5	1.0 mg plecanatide	2	2.0 mg plecanatide	30
B	12 to < 18 yrs. old	6	1.5 mg plecanatide	2	3.0 mg plecanatide	30
B	12 to < 18 yrs. old	7	Matching placebo	2	placebo	30

The study will be performed in a double-blind manner. All study drugs will be supplied in identical blister packs and tablets will be similar in color, smell, taste, and appearance, thereby assuring double-blind conditions.

The gender-stratified randomization schedule was prepared by Foehl Statistics & Analytics LLC.

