5.2.4.3. Time to First BM

For the time to first BM endpoint, the distribution for each treatment group within each age group, combined active doses within age group, and overall active doses will be estimated by the Kaplan-Meier method and will be compared by the Log-rank test. The median and quartile time along with the 95% confidence limits for the median will be presented for each treatment group.

Kaplan-Meier curves with 95% confidence limits will also be presented graphically by treatment group (Age group A and B with Placebo on one page, and Combined age group with Placebo on a second page).

The above analysis will be repeated for the PP Population.

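### Rescue tablets are compared by an unadjusted Wilcoxon test although baseline rescue use and the gender stratum are available: valid within an age group, but some precision is given up

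*Combined protocol and SAP*

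**What the plan says.** Protocol section 8.8.2.5 defines the outcome as a tablet count: "The number of tablets of rescue medication used per week, and overall, for the 4-week treatment period will be analyzed by treatment group". SAP section 5.2.4.5 keeps this and adds the proportion of subjects using any rescue. It specifies the test as follows: "The Mann Whitney U Test (Wilcoxon Rank Sum Test) will be used to compare the difference between each treatment group". The comparisons with placebo cover each dose, the combined doses within each age group and all active doses overall, week by week and over four weeks. Neither section names a covariate or a stratum.

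A baseline count can be derived. Protocol section 4.2.1 states: "Patients/caregivers will report the use of provided rescue medication (Dulcolax®), including time of use and amount of rescue medication used". Protocol section 3.2, item 24, uses the baseline diary to exclude on "Use of rescue medication (Dulcolax®, bisacodyl) for more than 2 days during either of the two weeks of the 2-week baseline diary assessment". The baseline definitions in SAP section 3.3.7 list the other diary measures but not rescue use.

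On allocation, SAP section 3.2 says: "Central, block randomization will be performed with stratification by gender". The ratio is 1:1:1 in the younger group and 1:1:1:1 in the adolescents.

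For time to first BM, SAP section 5.2.4.3 says that the groups "will be compared by the Log-rank test", again with no stratum.

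**The concern.** The mixed-model efficacy endpoints in SAP section 5.2 all adjust for gender and for their own baseline. That includes fecal incontinence, which is also a diary count. The protocol synopsis describes the secondary efficacy analysis in general as an ANCOVA with gender and the corresponding baseline value. Rescue use departs from this pattern and no reason is given.

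If a child's laxative use before treatment predicts use during treatment, the unadjusted test carries between-child variation that could be removed with data already collected. Each dose comparison has about 30 children per arm, so that variation matters more there. At stake is the chance of seeing a real effect on rescue use. The overall comparison has a further feature: age mix differs between the pooled active and pooled placebo arms, and Protocol section 3.3.1 permits different tablet numbers by age.

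**Working it through.** **The plan's own figure.** The only power figure is 81.5% for SBM frequency (Protocol section 8.2, SAP section 3.1). With 102 versus 34 patients, difference 1.5 and SDs 3.5 and 2.3:

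- SE = √(3.5²/102 + 2.3²/34) = 0.525
- power = Φ(1.5/0.525 − 1.96) = 0.815 at two-sided 0.05

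It reproduces, which shows that the printed 0.05% level is a slip for 0.05 (at 0.0005 the power would be 26.6%). It says nothing about rescue use, for which no power is claimed.

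**Step 1: baseline adjustment in general.** With correlation ρ between baseline and outcome, adjustment multiplies the residual variance by 1 − ρ². The gain in effective sample size is 1/(1 − ρ²) − 1.

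| ρ | 0.1 | 0.2 | 0.3 | 0.4 | 0.5 | 0.6 |
|---|---|---|---|---|---|---|
| Gain | 1% | 4% | 10% | 19% | 33% | 56% |

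**Step 2: simulated power for skewed tablet counts.** Assumptions: rate ratio 0.6 on drug, 2,000 trials per setting, gender rate ratio 1.0 in the first row of each block and 1.5 in the others. The middle column is the gender-stratified Wilcoxon (van Elteren); the next is gender-stratified rank ANCOVA on baseline tablets.

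| Active vs placebo | Rank correlation | Plain Wilcoxon | Gender strata only | Gender strata + baseline | Total gain (points) |
|---|---|---|---|---|---|
| 30 vs 30 | 0.11 | 44.7% | 44.2% | 43.8% | −0.9 |
| 30 vs 30 | 0.42 | 32.1% | 32.9% | 37.6% | +5.5 |
| 30 vs 30 | 0.56 | 23.0% | 23.5% | 31.1% | +8.1 |
| 90 vs 30 | 0.11 | 62.9% | 63.1% | 62.3% | −0.6 |
| 90 vs 30 | 0.41 | 44.5% | 45.2% | 51.2% | +6.7 |
| 90 vs 30 | 0.56 | 32.8% | 33.6% | 43.8% | +11.0 |

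Over all settings run, gender strata alone moved power by −0.5 to +1.7 points. Type I error was 3.8% to 6.0% for the three tests, with simulation error of about 0.5 point.

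**Step 3: respecting the limit on rescue days.** Children with more than two rescue days in a baseline week are excluded, and Protocol section 3.3.1 expects no more than two days in any week. Gamma-Poisson counts were simulated with that exclusion applied, on-treatment weeks capped at 2 and a 40% reduction. For the four-week total at 90 versus 30:

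| Assumed mean per week, gamma shape | Wilcoxon | Rank ANCOVA on baseline | Gain (points) |
|---|---|---|---|
| 0.8, 1 | 41.6% | 49.7% | 8.1 |
| 0.5, 0.7 | 30.8% | 34.6% | 3.8 |
| 1.0, 2 | 65.6% | 71.5% | 5.9 |

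At 30 versus 30 the gains were about 3 to 8 points. For a single week, or for the total at a correlation near 0.2, they were about 0 to 2 points. Type I error stayed near 5%.

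**Step 4: the overall comparison.** Active is 60 children + 90 adolescents, so 90/150 = 60% adolescents. Placebo is 30 + 30, so 50%. With no drug effect, the pooled mean difference is (0.60 − 0.50) × (adolescent mean − child mean). Assuming a child mean of 3 tablets and an adolescent-to-child ratio of 1.5 to 2.0, this is 0.1 × 1.5 = 0.15 to 0.1 × 3 = 0.30 tablets. Simulated rejection under no effect was 5.3% to 5.6% unstratified and 4.6% to 4.9% stratified by age. The distortion is small, but a stratum removes it.

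**The case against.** The strongest reply is that nothing is invalid. Within an age group the Wilcoxon test holds its error rate, and chance imbalance in baseline use is sampling error that the test already allows for. Rescue use is one of eight listed secondary endpoints in a trial the SAP calls exploratory, without multiplicity control. It is also not defined as a change from baseline, so the parallel with the mixed-model endpoints is imperfect. All of this stands, and it limits the weight of the point.

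The size is also open to challenge. A strong correlation between baseline and on-treatment use is plausible but undocumented, and at about 0.11 the gain vanishes. A reader might infer gains of 10 to 14 points, which the three Step 3 settings give when the two-day limit is not applied strictly (45.8% to 59.6%, 30.6% to 40.5%, 68.5% to 78.9%). The eligibility rule narrows the baseline range, so the documents do not support that reading.

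A reader might also infer that this test is a main support for the SBM result, because rescue intake decides which bowel movements are spontaneous. Protocol section 4.2.1 does not support that. The classification uses each recorded intake, and only that aspect of rescue use enters the primary endpoint. Changing the tablet test changes no SBM.

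Finally, SAP section 3.3.4 sets missing rescue use to zero. That is a separate problem, and adjustment would not cure it.

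**Conclusion.** The point holds as a modest efficiency issue. The plan leaves a recorded baseline and the randomisation stratum out of the rescue-use test, without a stated reason, when a rank-based adjusted test would keep the Wilcoxon's robustness to skewed, zero-heavy counts.

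The gain is roughly 0 to 11 points of power for the four-week total, and about 4 to 8 points at 90 versus 30 with the two-day limit respected. It is little for single weeks. These figures assume a 40% reduction, baseline rank correlations of about 0.1 to 0.55, and the use rates shown; none of these is in the documents. Nearly all of the gain comes from baseline. Gender strata are justified mainly because they match the randomisation.

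In the overall comparison, age group should be a stratum because the arms differ in age mix. For the log-rank test, stratification is a matter of consistency with the design; no loss of precision has been shown.

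**What to change.** - Add baseline rescue tablets per week to SAP section 3.3.7, derived from the last 14 diary days before Day 1, with a stated rule for missing diary days.
- In SAP section 5.2.4.5, replace the Wilcoxon by rank ANCOVA of tablets on baseline tablets, stratified by gender, for each week and for the four-week total. For all active doses versus placebo, stratify by gender and age group.
- Keep the plain Wilcoxon as a supportive analysis.
- In SAP section 5.2.4.3, stratify the log-rank test by gender, and also by age group for the overall comparison.

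The cost is SAP wording and a few lines of code; no new data are needed. Protocol section 8 lets the SAP set non-primary methods, provided this is done before database lock and unblinding.
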